Observational Study Protocol
**INVESTIGATING SECULAR TRENDS IN THE SURVIVAL OF
MELANOMA PATIENTS IN ENGLAND**

Study Investigators

Bristol-Myers Squibb

[name]

Bristol-Myers Squibb Research and Development
[name]
[name]
[name]
United Kingdom

Evidera

[name]
[name]
[name]

Evidera
[name]
[name]
[name]
United Kingdom

This document is the confidential and proprietary information of Bristol-Myers Squibb Company and its global affiliates (BMS). By reviewing this document, you agree to keep it confidential and to use and disclose it solely for the purpose of assessing whether your organization will participate in and/or the performance of the proposed BMS-sponsored study. Any permitted disclosures will be made only on a confidential "need to know" basis within your organization or to your independent ethics committee(s). Any other use, copying, disclosure or dissemination of this information is strictly prohibited unless expressly authorized in writing by BMS. Any supplemental information (e.g., amendments) that may be added to this document is also confidential and proprietary to BMS and must be kept in confidence in the same manner as the contents of this document. Any person who receives

this document without due authorization from BMS is requested to return it to BMS or promptly destroy it. All other rights reserved.

DOCUMENT HISTORY

Document	Date of Issue	Summary of Change
Original Protocol	26-Nov-18	Not Applicable

SYNOPSIS

Observational Study Protocol

Protocol Title: Investigating Secular Trends in the Survival of Melanoma Patients in England

Department: Centre for Observational Research and Data Science (CORDS)

Objective(s): The primary objectives of this study are to:

- (1) Describe the demographic and clinical characteristics of patients diagnosed with malignant melanoma
- (2) Describe trends in one-year overall and net survival over time among the overall population of malignant melanoma patients and among subgroups of interest (disease stage and socioeconomic status [SES])
- (3) Model changes in survival over time among these patients

Study Design: Observational cohort study

Study Population: Patients aged 18 years and above who were diagnosed with malignant melanoma at any stage from 1 January 1985 to 31 December 2015 will be identified from English Cancer Registry data held by Public Health England (PHE). The study period will span from 1 January 1985 until the latest available data (currently projected to be 31 December 2016). The study index date will be set as the date of initial diagnosis with malignant melanoma. The follow-up period will start on the day following the index date and will continue until death or end of the study observation period (December 31, 2016 or the date of most recent available data, whichever is latest). Patients with unknown gender or whose malignant melanoma diagnosis occurred at autopsy will be excluded. Patients will be further stratified into subgroups according to stage at diagnosis (as available) and SES.

Data Collection Methods: We will utilise existing cancer registration data from PHE. The cancer registration dataset includes data on demographics, characteristics of the tumour, patients' vital status and basic information regarding the treatment received. This information is submitted by National Health Services (NHS) providers to National Cancer Registration and Analysis Service (NCRAS) on a monthly basis in line with the requirements of the national standard for reporting cancer data, the Cancer Outcomes and Services Dataset (COSD).

Data Analyses: Descriptive statistics will be used to summarise the demographic and clinical characteristics of the overall population as well as for the subgroups of interest. Variables anticipated to be key predictors of survival (age and stage at diagnosis) will also be presented stratified by calendar year. The number and percentage of deaths will be presented stratified by calendar year. The non-parametric Kaplan-Meier (KM) method will be used to estimate overall one-year survival, and one-year net survival will be estimated as the relative survival, i.e., the ratio of observed to expected survival. Observed survival will be estimated using life-table methods and an actuarial estimator. The expected survival will be derived from published life-tables. Estimates of the RS will be age-standardised to the international standard cancer patient population. Trends in the relative survival will be modelled in the framework of generalized linear models (GLMs) using a Poisson assumption for the observed number of deaths, with models stratified by subgroups of interest. Trends in overall survival will be modelled using Cox proportional hazards models. To model a potential non-linear relationship between the survival and calendar year of diagnosis, smoothing functions such as restricted cubic splines (fractional polynomials) will be used.

Sample Size/Power: All eligible patients will be included. As the dataset has nationwide coverage, all statistics will be calculated directly using the entire population of interest, rather than a sample. Because of this there is no sampling variation, and sample size calculations are therefore not applicable.

Limitations/Strengths: Analyses of changes in cancer survival over time can be susceptible to lead-time bias and bias due to stage migration as a result of improved diagnostics; findings will need to be interpreted bearing such limitations in mind. In addition, the dataset contains limited information regarding the medical history of patients. It is also important to note that changes in survival over time can have multiple explanations, and these analyses will not attempt to identify causal effects.

1 INTRODUCTION

1.1 Study Rationale

Melanoma, also known as malignant or cutaneous melanoma, is a type of skin cancer that arises from the uncontrolled proliferation of pigmented skin cells, melanocytes. It is the fifth-most common cancer in the UK, accounting for nearly 4% of all new cancer cases.¹ Over the last decade, the incidence of melanoma has increased by more than 50% in the UK, with rates in males and females increasing with 64% and 39%, respectively². These incidence rates are further projected to rise by 7% between 2014 and 2035.³ Survival rates for melanoma vary depending of the stage of the disease. According to the UK Office of National Statistics (ONS), one-year net survival for melanoma is indistinguishable from that in the general population among patients diagnosed at stage I, but considerably lower among those diagnosed at stage IV.⁴ Studies suggests that patients with stage IV melanoma have a median survival of just 6 to 10 months.⁵

While surgery and radiation therapy are effective for patients with localised and regional melanoma, metastatic or late-stage melanoma patients do not respond well to these treatment options.⁶ The development of gene targeted and immuno-oncology (IO) treatments, such as BRAF inhibitors (e.g., vemurafenib, dabrafenib, and encorafenib), MEK inhibitors (e.g., trametinib, cobimetinib and binimetinib), cytotoxic T-lymphocyte-associated antigen-4 (CTLA-4) blockers (e.g., ipilimumab) and programmed-death-1 (PD-1) inhibitors (e.g., nivolumab and pembrolizumab) have transformed the treatment options available to melanoma patients.⁷ These agents have raised survival expectations and shifted the treatment paradigm for metastatic melanoma.⁸

Despite both IO and gene targeted melanoma treatments showing good efficacy in the clinical trial setting⁹, there are few studies evaluating the public health impact of these treatments by considering outcomes on a population level. One retrospective study utilised the National Cancer Database in the United States (US) from 2004-2015 to evaluate the impact of targeted therapies and IO agents, first approved by the Food and Drug Administration (FDA) in 2011, on survival among stage IV melanoma patients. The findings of the study demonstrated a 31% relative increase in 4-year overall survival among patients diagnosed after 2011 compared to patients diagnosed prior to 2011.¹⁰

Our study aims to provide a detailed evaluation of melanoma survival over time in England. As previous studies have shown that melanoma survival varies significantly according to patient demographic characteristics, and particularly socioeconomic status (SES)^{11,12}, we will also evaluate whether any observed changes over time vary within different subgroups, specifically disease stage and SES.

Research Question

The research question is:

1. What are the trends in survival over time among patients with malignant melanoma, and do these trends vary according to disease stage or the socioeconomic status of patients?

2 OBJECTIVES

2.1 Primary Objectives

The specific objectives of this study are to:

1. Describe the demographic and clinical characteristics of patients diagnosed with malignant melanoma
2. Describe trends in one-year overall and net survival over time among the overall population of malignant melanoma patients and among subgroups of interest (disease stage and SES)
3. Model changes in survival over time among these patients

2.2 Secondary Objectives

Not Applicable.

2.3 Exploratory Objectives

Not Applicable.

3 STUDY DESIGN

[figure not shown]
3.1 Overview of Study Design

This is an observational cohort study of patients diagnosed with malignant melanoma using cancer registration data from Public Health England (PHE).

3.2 Study Population

The study population will include patients diagnosed with malignant melanoma at any stage from 1 January 1985 to one year prior to the end of available data (currently assumed to be 31 December 2015) using ICD-10 codes (Table 1).

The study period will span from 1 January 1985 until the latest available data (currently assumed to be 31 December 2016). The study index date will be set as the date of initial diagnosis with malignant melanoma. The follow-up period will start on the day following the index date and will continue until death or the end of the study observation period (31 December 2016 or the date of most recent available data, whichever is latest). Figure 1 below further illustrates the study periods.

Figure 1. Study Design

3.2.1 Inclusion Criteria

Patients will be included in the study if they meet all of the following criteria:

1. Patients with an ICD-10 code for malignant melanoma
2. Patients aged 18 years or above at their index date

Codes which will be used to identify the population are shown in Table 1.

Table 1. Codes used to identify patients with melanoma

ICD-10 code	Description
C43	Malignant melanoma of skin
C43.0	Malignant melanoma of lip
C43.1	Malignant melanoma of eyelid, including canthus
C43.2	Malignant melanoma of ear and external auricular canal
C43.3	Malignant melanoma of other and unspecified parts of face
C43.4	Malignant melanoma of scalp and neck
C43.5	Malignant melanoma of trunk
C43.6	Malignant melanoma of upper limb, including shoulder
C43.7	Malignant melanoma of lower limb, including hip
C43.8	Overlapping malignant melanoma of skin
C43.9	Malignant melanoma of skin, unspecified

3.2.2 Exclusion Criteria

Patients will be excluded if they meet any of the following criteria:

1. Unknown gender

2. Patients whose melanoma diagnosis occurred at autopsy

3.2.3 Subgroups of Interest

The two subgroups of interest are stage at diagnosis and SES.

- **Disease Stage:** Disease stage at index:
 - Stage 0
 - Stage I
 - Stage II
 - Stage III
 - Stage IV

Disease stage has only been recorded consistently in NCRAS data since 2012. Analyses in early calendar years may therefore be limited to descriptive assessments within the subset of patients who have this data available.

- **SES:** Estimates of SES will be based on the index of multiple deprivation (IMD). This index has seven domains of deprivation—income, employment, health and disability, education, crime, barriers to housing and services, and living-environment.¹³ Data on IMD is provided as quintiles of IMD, from least to most deprived. Depending on the number of people available within each IMD strata, it may be necessary to group the IMD strata together to allow for analyses.

3.3 Data Source

This study will utilise cancer registration data from PHE. PHE's National Cancer Registration and Analysis Service (NCRAS) is responsible for maintaining a population-based registry of all cases of cancer diagnosed and/or treated in England. NCRAS routinely collects both patient and tumour-level data from more than 500 local and regional datasets. The cancer registration data tables include data on the patient, their diagnosis, tumour characteristics and details of the care and treatment received. This information is submitted by NHS providers to NCRAS on a monthly basis in line with the requirements of the national standard for reporting cancer data, the Cancer Outcomes and Services Dataset (COSD).¹⁴

Specific information provided in the cancer registration data includes the following:

1. Patient tables: Variables include sex, ethnicity, vital status, and cause of death
2. Tumour tables: Variables include age at diagnosis and tumour-related information, such as tumour site and grade, morphology, and histology

Data is available from the 1 January 1985, and there is an approximate one-year lag time between dataset updates.

3.4 Definitions of Study Variables

3.4.1 Outcomes/Endpoint Variables

The primary outcomes of interest in this study are overall and relative survival¹⁵. Definitions of both the OS and RS are provided in Table 2.

Table 2. Outcome Definitions

Outcome/Endpoint	Definition	Timing
Overall Survival (OS)	Time since the index date (initial diagnosis) +1 until date of death due to any cause. Individuals still alive at the end of follow-up will be censored at the last day of available data.	From the day after index until the last day of available data (during follow-up)
Relative Survival (RS)	RS is defined as the ratio of observed to expected survival, expressed as a percentage. Observed survival at one-year post index will be estimated using the life table method with an actuarial estimator. The expected survival will be estimated using life tables published by the ONS ¹⁶ . The RS will consequently be age-standardised to the international standard cancer patient population. ¹⁷	From the day after index until the last day of available data (during follow-up)

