3.4.3 Other Covariates/Control Variables

Several demographic and clinical characteristics will be examined in the study cohort. They are summarised in Table 4.

Table 4. Covariate Definitions

Covariate	Categories	Definition	Timing
Ethnicity	White, Non-White or Unknown	Derived using the “Ethnic Group” variable, as follows: White = A (White British), B (White Irish), C (Any Other White Background); Unknown = Z (Not stated), X (Not known) Non-white = All other categories	At index date
Sex	Male, Female or Unknown	Derived using the variable “Sex”, as follows: 1=Male 2=Female	At index date
Vital Status	Alive, Dead or Exit posting	Derived using the “vitalstatus” variable, as follows: A =Alive, D =Dead, X =Exit posting	During follow-up
Age at Diagnosis	0–4 yrs., 5–9 yrs., 10–14 yrs., 15–19 yrs., 20–24 yrs., 25–29 yrs., 30–34 yrs., 35–39 yrs., 40–44 yrs., 45–49 yrs., 50–54 yrs., 55–59 yrs., 60–64 yrs., 65–69 yrs., 70–74 yrs., 75–79 yrs., 80–84 yrs.	Derived using the “fiveyearageband” variable	At index date
SES	1 (least deprived) to 5 (most deprived)	Derived using the IMD quintile variable	At index date

Covariate	Categories	Definition	Timing
Basis of Tumour Diagnosis	Categorisation to be determined in collaboration with NCRAS	Derived using the “basisofdiagnosis” variable to exclude cases diagnosed via autopsy or death certificate	At index date
Site of Tumour	Categorisation to be determined in collaboration with NCRAS	Derived using the “site_ICD10_O2” variable to capture location of malignant melanoma	At index date
Morphology of the Cancer	Categorisation to be determined in collaboration with NCRAS	Derived using the “morph_ICD10_O2” variable to enable description of malignant melanoma	At index date
Behaviour of the Cancer	Categorisation to be determined in collaboration with NCRAS	Derived using the “behavior_ICD10_O2” variable to enable description of malignant melanoma	At index date
T stage	Categorisation to be determined in collaboration with NCRAS	T stage flagged by the registry as the ‘best’ T stage, derived using the variable T_BEST	At index date
N stage	Categorisation to be determined in collaboration with NCRAS	N stage flagged by the registry as the ‘best’ N stage	At index date
M stage	Categorisation to be determined in collaboration with NCRAS	M stage flagged by the registry as the ‘best’ M stage	At index date
Tumour Grade	Well differentiated, moderately differentiated,	Derived using the “grade” variable, as follows:	At index date

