8 GLOSSARY OF TERMS AND LIST OF ABBREVIATIONS

8.1 Glossary of Terms

Term	Definition
Overall Survival	Overall survival is defined as the length of time between a defined time-point, such as the date of diagnosis of a condition, and the date of death. This is commonly presented as the proportion of patients still alive by a given time-point, estimated using non-parametric methods such as the Kaplan-Meier estimator.
Net survival	Net survival is a hypothetical measurement, defined as patient survival corrected for the effect of other causes of death. In registry studies, net survival is commonly estimated through the calculation of relative survival, both due to the absence of reliable cause of death information as well as the inherent challenges of determining a single cause of death for many patients.
Relative Survival	Relative survival is the ratio of the observed survival rate in a population to the expected survival rate of a similar cohort of people in the general population; matched on age, sex and year of observation. It is commonly expressed as a percentage. It is often used to estimate net or “excess” mortality due to a specific condition, such as cancer, when cause of death information is not known or poorly recorded.
Lead-time bias	Lead-time bias refers to the bias introduced into studies of survival due to the progressively earlier diagnosis of a condition, e.g., due to the introduction of screening.
Stage migration	Stage migration refers to the tendency for cancers to be diagnosed as late-stage or metastatic more readily in later calendar years, due to the use of more sensitive diagnostics or updated staging systems.

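### Follow-up starts the day after diagnosis and has no end date for exit postings, so same-day deaths have no valid survival time and leavers remain at risk (minor)

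*Protocol*

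**What the plan says.** **Time origin.** Protocol Table 2 measures overall survival (OS) as "Time since the index date (initial diagnosis) +1 until date of death due to any cause". The timing column, for both OS and relative survival (RS), starts on the day after index. Section 3.2 agrees: "The follow-up period will start on the day following the index date and will continue until death or the end of the study observation period". The Synopsis repeats the rule.

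**Eligibility.** Section 3.2.2 excludes unknown gender and diagnosis at autopsy. Table 4, under basis of diagnosis, adds death-certificate cases. Neither removes a patient diagnosed in life who dies on the day of diagnosis.

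**End of follow-up.** The only censoring rule is in Table 2: "Individuals still alive at the end of follow-up will be censored at the last day of available data". Table 4 (section 3.4.3) gives vital status three values, "A =Alive, D =Dead, X =Exit posting", but no date is attached to the third. The actuarial estimator in section 4.1.1 subtracts half of those censored within the year.

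**Data end.** Section 3.2 and the Synopsis set the end of observation as "31 December 2016 or the date of most recent available data, whichever is latest". Table 2 uses the last day of available data.

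**The concern.** A death on the diagnosis date falls before the first day of follow-up, yet the patient meets every eligibility criterion. The RS denominator in section 4.1.1 counts people under follow-up at the start of the interval, and this patient is not among them. If such deaths are lost from the survival estimates, survival is overstated. The table of deaths by calendar year required by section 4.1.1 may then not reconcile with the survival results.

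An exit posting is neither a death nor a patient known to be alive. With no exit date in the rules, that person is carried to data end, counted at risk, and cannot be observed to die. This also raises survival, and more so as follow-up lengthens.

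Both rules are stated in the protocol, so an analysis plan that followed them would inherit the problem.

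**Working it through.** The protocol states no survival, event or sample-size figure, so there is nothing to reproduce. The check is date arithmetic plus bounds under stated assumptions.

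**1. Time from index+1.**
- Death on the index date: −1 day.
- Death on the next day: 0 days.
- Death two days after index: 1 day.

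If index+1 is instead numbered day 1, a same-day death is day 0, still before follow-up begins. Table 2 read alone could mean (death − index) + 1, which would give a same-day death a time of 1. The timing column and section 3.2 rule that out.

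**2. Effect of losing same-day deaths.** Let S be true one-year survival and s the share who die on the day of diagnosis. Dropping them gives S/(1−s), so the bias is S·s/(1−s). Assumed inputs, neither in the protocol: S = 0.96; s = 0.1% to 0.5%.
- s = 0.001: 0.96 × 0.001/0.999 = 0.00096, or 0.10 points.
- s = 0.005: 0.96 × 0.005/0.995 = 0.00482, or 0.48 points.

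Taking S = 0.97 gives 0.10 and 0.49 points. With expected survival held fixed, RS rises by the same factor, 1/(1−s).

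**3. Who can be censored within a year?** The last diagnosis date is 31 December 2015 and data are assumed to end on 31 December 2016. From index+1 (1 January 2016) that is 365 days. Nobody is administratively censored within 365 days, so under Table 2 the half-censored term has nothing to subtract. Only exits or untraced patients could supply it.

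**4. Exits at one year.** Section 6.2 puts untraced patients below 0.3%. Assume this covers exit postings, so the leaving share is c = 0.003.
- Exits spread evenly over the year: bias (1−S)·c/2 = 0.04 × 0.0015 = 0.00006, or 0.006 points.
- All exits on day 0 (upper bound): (1−S)·c = 0.04 × 0.003 = 0.00012, or 0.012 points.

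This term grows as S falls, but at S = 0.25 the evenly spread case is still only 0.75 × 0.0015, or 0.11 points.

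**5. Exits over long follow-up.** Table 2 runs follow-up to data end, so this matters if the Cox models use all of it. Assume a constant hazard h = 0.04 per year, T = 30 years, and exits spread evenly over T. A leaver at time u is wrongly counted as alive at T with probability 1 − exp(−h(T−u)). The average over u is 1 − (1 − exp(−hT))/(hT) = 1 − (1 − 0.301)/1.2 = 0.418.
- At 0.3%: 0.003 × 0.418 = 0.00125, or about 0.13 points.

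**The case against.** The strongest reply is that the protocol nowhere says same-day deaths are discarded, and that handling of zero or negative times is normally left to the analysis plan. The first half stands: the drop-out is an inference, and the sizes above are conditional on it. The second half stands only in part, because the protocol itself fixes the origin at index+1. Autopsy and death-certificate exclusions also remove the most obvious date-of-death registrations, so the remaining share may be small.

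On exits, one can argue that the half-censored term, together with a vital status of "Alive, Dead or Exit posting", shows earlier censoring was intended. That is plausible, but section 3.2 still ends follow-up only at death or the end of observation.

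On trends, a constant offset largely cancels. It would distort a trend only if the same-day share changed over 1985–2015, and the documents do not say that it did.

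A reader might infer several stronger points that the documents do not support:
- **A larger same-day bias in stage IV.** At an equal share the gain in points is smaller where survival is low: at s = 0.5%, 0.13 points at S = 0.25 against 0.48 at S = 0.96. The claim needs a higher stage IV same-day share, which is not given.
- **A contradiction with the glossary.** Section 8.1 describes "the length of time between a defined time-point, such as the date of diagnosis of a condition, and the date of death". That is a generic example, not a competing rule.
- **A known software consequence.** Section 4.1.1 names Stata and SAS but says nothing about how either treats such times.
- **A large exit effect.** Assuming 2% leave, all on day 0, gives 0.02 × (1 − 0.301), or 1.4 points at 30 years. The 2% has no source, and even exits spread evenly would give 0.02 × 0.418, or 0.84 points.

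**Conclusion.** The point holds as a minor defect. The stated origin leaves eligible same-day deaths without a valid time. The stated end of follow-up leaves exit postings at risk, which does not fit the protocol's own vital-status categories or its actuarial estimator.

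If same-day deaths are lost, one-year survival is overstated by about 0.1 to 0.5 points. That range rests on an assumed same-day share of 0.1–0.5% and assumed survival of about 0.96. The exit effect is about 0.01 points or less overall at one year. It is about 0.13 points at 30 years with exits evenly spread and a 4% annual hazard. Both exit figures assume that the 0.3% ceiling covers exits.

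The phrase about whichever date is latest is loose wording. It conflicts with Table 2 only if data end before 31 December 2016, and no bias is attributed to it here.

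**What to change.** In Table 2, section 3.2 and the Synopsis:
- Start survival time at the date of diagnosis.
- Exclude autopsy and death-certificate cases, listing both in section 3.2.2, then keep the remaining same-day deaths as events by a stated convention, for example 0.5 day.
- Censor exit postings at the exit date.
- Replace the whichever-is-latest wording with the last date to which vital status is complete, to agree with Table 2.

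Reporting the number of same-day deaths and exit postings by year of diagnosis would replace the assumed shares with observed ones. The cost is a few lines of wording and one extra field, the exit-posting date, in the data request.
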